19.0 Safety Monitoring

The study protocol will be reviewed and approved by the National Institutes of Health (NIH) before submission to University of Minnesota IRB for approval. Participant enrollment may only proceed with IRB approved consent forms. All adverse events will be reported to the local IRB and to the Study Chair who will tabulate and review these events.

The Study Chair has primary oversight responsibility of this clinical trial. The Study Chair and the Steering Committee will review accrual patterns, adverse events, data quality, and protocol compliance.

19.1 Data and safety monitoring plan. The NINDS has reviewed the risk associated with this study, and the following safety monitoring will be implemented:

The Study Chair and her IRB will monitor the study and all adverse events. In addition, adverse event reports will be sent to the ORDR-designated medical monitor on a basis to be agreed upon, generally monthly. The ORDR-designated medical monitor will also review cumulative adverse events (AEs). The frequency of review of cumulative AEs will be determined by the medical monitor in conjunction with the Study Chair and will occur at least every 12 months.

The Study Chair has primary oversight responsibility of this clinical trial. The investigators will identify adverse events on an ongoing basis as they occur and will report them to the IRB and the Data Management and Coordinating Center (DMCC). If a subject experiences an adverse effect from the treatment medication, dose reduction adjustments will be made to the medication, if indicated.

The Principal Investigator and the research team (co-investigators, research nurses, clinical trial coordinators, and data managers) are responsible for identifying adverse events. Aggregate report—detailed by severity, attribution (expected or unexpected), and relationship to the study procedures—will be available from the DMCC for site review. Adverse events will be reviewed by the research team as they occur. A separate report detailing protocol compliance will also be available from the DMCC for site review on a monthly basis. The research team will then evaluate whether the protocol or informed consent document requires revision based on the reports.

19.2 Adverse event definitions and standards. The Rare Diseases Clinical Research Network defines an adverse event as: "...an unfavorable and unintended sign, symptom or disease associated with a participant's participation in a Rare Diseases Clinical Research Network study."

Serious adverse events include those events that: "result in death; are life-threatening; require inpatient hospitalization or prolongation of existing hospitalization; create persistent or significant disability/incapacity, or a congenital anomaly/birth defect."

An unexpected adverse event is defined as any adverse experience...the specificity or severity of which is not consistent with the risks described in the protocol.

Expected adverse events are those that are known to be associated with or have the potential to arise as a consequence of participation in the study.

All reported adverse events will be classified using the current version of the Common Terminology Criteria for Adverse Events (CTCAE) developed and maintained by CTEP at National Cancer Institute.

19.3 Expected and known risks, discomforts, or adverse events associated with study intervention and procedures: Definition of expected adverse events. Neuropsychological testing: No known risks. No sensitive questions will be asked during the testing.

Anticipated risks of miglustat.²³ Potential risks to subjects include the following adverse drug events:

In clinical trials of miglustat in children with gangliosidoses, miglustat demonstrated an acceptable safety profile for use in young children. The most common side effects reported

were diarrhea and weight loss. These gastrointestinal side effects of miglustat may be prevented or ameliorated by using a low-carbohydrate diet.

In clinical trials of adult patients with Gaucher disease type I, common side effects reported included:

- Diarrhea (up to 100% of patients of patients with adult Gaucher disease type I)
- Flatulence (29-50% of patients of patients with adult Gaucher disease type I)
- Weight loss (39-67% of patients of patients with adult Gaucher disease type I)
- Abdominal pain (18-67% of patients of patients with adult Gaucher disease type I)
- Tremor (11-30% of patients with adult Gaucher disease type I)

Miglustat risk mitigation. Risks of gastrointestinal side effects may be mitigated by implementation of a ketogenic diet that may minimize or reduce the severity of food-drug interactions between carbohydrates and miglustat.

Anticipated risks of the ketogenic diet. The ketogenic diet has been safely used in children and adults for many decades.²⁸⁻³⁰ Patients may experience constipation with use of the ketogenic diet, especially during the initiation phases of the ketogenic diet. The ketogenic diet may also cause increased urination, and this could lead to dehydration. Subjects may experience lethargy while transitioning to the ketogenic diet. The lethargy often resolves once the patient is established on the ketogenic diet, but in some patients it may continue. Patients should be monitored for hypoglycemia 2 to 3 times daily during the initiation of the ketogenic diet, more frequently during adjustments to the ketogenic diet, and then periodically after they are stabilized on the ketogenic diet, as deemed appropriate by the patient's clinical ketogenic diet team. A very rare occurrence of kidney stones in patients using the ketogenic diet has raised a concern about the possibility of an increase in risk of kidney stone development.²⁸⁻³⁰ Increased risk of kidney stones has been associated with anti-seizure medications that have carbonic anhydrase inhibiting action, such as acetazolamide and topiramate.³¹ Some patients have experienced a transient increase in seizures during the initiation of the ketogenic diet.²⁸⁻³⁰

Risk mitigation of the ketogenic diet. The ketogenic diet will be managed by a clinical ketogenic diet team that includes ketogenic dietician(s), neurologist, pharmacist and clinical geneticist, specially trained in the implementation and maintenance of the ketogenic diet. The ketogenic dietitian will make recommendations for ordering of nutrition labs and lipid labs prior to beginning ketogenic diet and as clinically indicated (e.g. lipid panel, comprehensive metabolic panel, transferrin, pre-albumin, vitamin levels for vitamin D and the B vitamins). Patients will be evaluated for signs of development of constipation or worsening of existing constipation, and will be treated as needed with medications for treatment/prevention of constipation. Subjects will be monitored for signs of dehydration per ketogenic dietitian recommendation, and will be treated as needed with appropriate hydrating fluids per ketogenic dietitian's clinical management and recommendations. Patients will also be monitored for signs of kidney stone development, such as signs of pain and/or difficulty urinating. Use of anti-seizure medications with carbonic anhydrase inhibiting action will be minimized and avoided if possible.³¹

There are no anticipated risks to investigators, lab personnel, and/or the environment.

19.4 Adverse event reporting timeline.

- Within **24 hours** (of learning of the event), investigators must report any reportable Serious Adverse Event (SAE) that:

- Is considered life-threatening/disabling or results in death of participant
- OR-
- Is Unexpected/Unanticipated
- Investigators must report all other reportable SAEs within **5 working days** (of learning of the event).
- All other (suspected) reportable AEs must be reported to the Rare Diseases Clinical Research Network (RDCRN) within **20 working days** of the notification of the event or of the site becoming aware of the event.

Local institutional reporting requirements to IRBs and the FDA remain the responsibility of the site investigator and the Study Chair.

19.5 RDCRN Adverse Event Data Management System (AEDAMS). Upon entry of a serious adverse event by the site investigator, the DMCC-created Adverse Event Data Management System (AEDAMS) will immediately notify the Study Chair, the site PI, and the Medical Review Officer of any reported adverse events via e-mail.

Serious adverse events. The NIH appointed Medical Review Officer (MRO) determines causality (definitely not related, probably not related, possibly related, probably related, definitely related) of the adverse event. The MRO may request further information if necessary and possibly request changes to the protocol or consent form as a consequence of the adverse event. A back-up notification system is in place so that any delays in review by the MRO beyond a specified period of time are forwarded to a secondary reviewer. The Adverse Event Data Management System (AEDAMS) maintains audit trails and stores data (and data updated) and communication related to any adverse event in the study.

Non-serious expected adverse events. Except those listed above as immediately reportable, non-serious expected adverse events that are reported to or observed by the investigator or a member of his research team will be submitted to the DMCC in a timely fashion (within 20 working days). The events will be presented in tabular form and given to the MRO on an annual basis or as requested. Local site investigators are also required to fulfill all reporting requirements of their local institutions.

The DMCC will post aggregate reports of all adverse events (serious/not serious and expected, unexpected) for site investigators and IRBs.

19.6 Unanticipated Problem Reporting. The Office for Human Research Protections (OHRP) considers unanticipated problems involving risks to subjects or others to include, in general, any incident, experience, or outcome that meets all of the following criteria:

- unexpected in terms of nature, severity, or frequency given
 - (a) the research procedures that are described in the protocol-related documents, such as the IRB-approved research protocol and informed consent document; and
 - (b) the characteristics of the subject population being studied;
- related or possibly related to participation in the research (“possibly related” means there is a reasonable possibility that the incident, experience, or outcome may have been caused by the procedures involved in the research); and
- suggests that the research places subjects or others at a greater risk of harm (including physical, psychological, economic, or social harm) than was previously known or recognized.

Per the definition, only a subset of adverse events would be characterized as unanticipated problems. There are other types of incidents, experiences, and outcomes that are not considered adverse events, but are characterized as unanticipated problems (e.g., breach of confidentiality or other incidents involving social or economic harm).

Incidents or events that meet the OHRP criteria for unanticipated problems are to be reported to the IRB, per local institutional reporting requirements. Local institutional reporting requirements to IRBs, any GCRC oversight committee and the FDA, if appropriate, remain the responsibility of the treating physician and the Study Chair.

20.0 Anticipated Risks

20.1 Anticipated risks of miglustat.²³ Potential risks to subjects include the following adverse drug events:

In clinical trials of miglustat in children with gangliosidoses, miglustat demonstrated an acceptable safety profile for use in young children. The most common side effects reported were diarrhea and weight loss. These gastrointestinal side effects of miglustat may be prevented or ameliorated by using a low-carbohydrate diet.

In clinical trials of adult patients with Gaucher disease type I, commonly reported side effects of miglustat included:

- Diarrhea (up to 100% of patients of patients with adult Gaucher disease type I)
- Flatulence (29-50% of patients of patients with adult Gaucher disease type I)
- Weight loss (39-67% of patients of patients with adult Gaucher disease type I)
- Abdominal pain (18-67% of patients of patients with adult Gaucher disease type I)
- Tremor (11-30% of patients with adult Gaucher disease type I)

20.2 Miglustat risk mitigation. Risks of gastrointestinal side effects may be mitigated by implementation of a ketogenic diet that may minimize or reduce the severity of food-drug interactions between carbohydrates and miglustat.

20.3 Anticipated risks of the ketogenic diet. The ketogenic diet has been safely used in children and adults for many decades.²⁸⁻³⁰ Patients may experience constipation with use of the ketogenic diet, especially during the initiation phases of the ketogenic diet. The ketogenic diet may also cause increased urination, and this could lead to dehydration. Subjects may experience lethargy while transitioning to the ketogenic diet. The lethargy often resolves once the patient is established on the ketogenic diet, but in some patients it may continue. Patients should be monitored for hypoglycemia 2 to 3 times daily during the initiation of the ketogenic diet, more frequently during adjustments to the ketogenic diet, and then periodically after they are stabilized on the ketogenic diet, as deemed appropriate by the patient's clinical ketogenic diet team. A very rare occurrence of kidney stones in patients using the ketogenic diet has raised a concern about the possibility of an increase in risk of kidney stone development.²⁸⁻³⁰ Increased risk of kidney stones has been associated with anti-seizure medications that have carbonic anhydrase inhibiting action, such as acetazolamide and topiramate.³¹ Some patients have experienced a transient increase in seizures during the initiation of the ketogenic diet.²⁸⁻³⁰

20.4 Risk mitigation of the ketogenic diet. The ketogenic diet will be managed by a clinical ketogenic diet team that includes ketogenic dietician(s), neurologist, pharmacist and clinical geneticist, specially trained in the implementation and maintenance of the ketogenic diet. The

ketogenic dietitian will make recommendations for ordering of nutrition labs and lipid labs prior to beginning ketogenic diet and as clinically indicated (e.g. lipid panel, comprehensive metabolic panel, transferrin, pre-albumin, vitamin levels for vitamin D and the B vitamins). Patients will be evaluated for signs of development of constipation or worsening of existing constipation, and will be treated as needed with medications for treatment/prevention of constipation. Subjects will be monitored for signs of dehydration per ketogenic dietitian recommendation, and will be treated as needed with appropriate hydrating fluids per ketogenic dietitian's clinical management and recommendations. Patients will also be monitored for signs of kidney stone development, such as signs of pain and/or difficulty urinating. Use of anti-seizure medications with carbonic anhydrase inhibiting action will be minimized and avoided if possible.³¹

There are no anticipated risks to investigators, lab personnel, and/or the environment.

21.0 Study Discontinuation

21.1 Discontinuation rules. The NIH and the University of Minnesota IRB have the authority to stop or suspend this study at any time. Additionally, the following study discontinuation rules apply:

- 1) That the rate of severe adverse events is such that continued participation would compromise subject safety.
- 2) Target subject accrual has not met, and cannot meet trial objectives.

21.2 Participant discontinuation. All data acquired prior to termination for the reasons outlined below will be included in the primary analysis unless patient withdraws consent. Every effort will be made to conduct a final study visit with the participant, and participants will be followed clinically until, if applicable, all adverse events resolve. Participant discontinuation in this study will occur for the following reasons:

- Participants who develop kidney function problems while in this study will be withdrawn from this study.
- Females who are able to become pregnant, and who are sexually active, must use a highly effective birth-control method to prevent pregnancy while in this study. If a participant becomes pregnant while in this study, they will be withdrawn from this study.
- If a patient develops bleeding due to low platelets while in this study, treatment with miglustat will be stopped.
- If a patient develops severe diarrhea and/or weight loss that cannot be managed by changing the ketogenic diet formula or lowering the miglustat dose, the patient will be removed from the study.
- Withdrawal of consent
- Withdrawal by the participant
- Withdrawal of the participant by the Investigator(s) (If a subject experiences an adverse effect from the treatment medication, dose reduction adjustments will be made to the medication, or the subject will be withdrawn from the study, if indicated.)

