12.0 Study Objectives

12.1 Primary objective. The primary analysis for Syner-G treatment regimen will use the intention-to-treat (ITT) population and evaluate overall survival. This will be evaluated based on chronological age at time of death or conclusion of study (whichever occurs first), and compared to available natural history data. Median survival will be compared to previously reported natural history studies of infantile⁹ and juvenile¹¹ forms. Median survival of patients with infantile GM2 gangliosidosis was estimated at 47 months based on data from the National Tay-Sachs and Allied Diseases database for patients born after 2000.⁹ Median survival for the juvenile form was estimated at 14.5 years.¹¹

12.2 Secondary objective. Evaluate the effect of Syner-G therapy in patients with infant and juvenile gangliosidoses on changes in neurodevelopmental status, as assessed using age-equivalent scores of the Bayley Scales of Infant and Toddler Development for expressive communication, receptive communication, fine motor skills and gross motor skills; and using the Vineland Adaptive Behavior Scales.

A secondary endpoint will be the rate of change (i.e., slope) in neurocognitive functioning over the duration of follow-up, compared to available natural history data. This analysis will be conducted separately for each of the two sub-types: infantile and juvenile. The primary neurocognitive functioning endpoint for both pediatric groups is age-equivalent scores of the Bayley Scales of Infant and Toddler Development for expressive communication, receptive communication, fine motor skills and gross motor skills. Another primary neurocognitive functioning endpoint for both pediatric groups is age-equivalent scores of the Vineland Adaptive Behavior Scales. Using general estimating equations (GEE) and an exchangeable working correlation structure, variance estimation for confidence intervals and P-values will take into

account the possible correlated nature of multiple measurements on the same individual. Supportive analyses will include evaluation using the per-protocol (PP) population.

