13.0 Study Design

13.1 Overview of study design. Both retrospective and prospective data will be collected during this study. This is a single-arm treatment protocol, with intention-to-treat per-protocol design. The primary analysis for Syner-G treatment regimen will use the intention-to-treat (ITT) population and evaluate overall survival. This will be evaluated based on chronological age at time of death or conclusion of study (whichever occurs first), and compared to available natural history data. This will be conducted separately for each of the two sub-types: infantile and juvenile. The neurocognitive functioning endpoint for both groups is the cognition domain of the Bayley Scales of Infant and Toddler Development for expressive communication, receptive communication, fine motor skills, gross motor skills; and the Vineland Adaptive Behavior Scales. Each of the other 4 domains will be evaluated as secondary endpoints. Using general estimating equations (GEE) and an exchangeable working correlation structure, variance estimation for confidence intervals and P-values will take into account the possible correlated nature of multiple measurements on the same individual. Supportive analyses will include evaluation using the per-protocol (PP) population.

Subgroup analyses: analyses will be repeated among GM1 gangliosidosis patients and among GM2 gangliosidosis patients, and among the infantile and juvenile forms of both GM1 and GM2 gangliosidosis.

Yearly evaluations, whenever possible, will also explore changes in seizure frequency and severity, and in movement disorders, evaluated by neurologist and parent-report.

Some subjects do not have insurance coverage for certain evaluations. Sometimes the insurance coverage changes and clinical care that was covered in the past is no longer covered. The investigators will continue to see these patients annually, whenever possible, and will provide the scheduled clinical-care visits according to what is allowed within the restrictions of the subject's health care insurance. When any given subject is unable to make their annual visit to the University of Minnesota due to illness or weakness, this will not cause them to be withdrawn from the research study. The reason for foregoing the evaluation will be documented in the subject's file, and the investigators will continue to follow them through telephone contacts with family members and health care providers.

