16.0 Subject Withdrawal

16.1 How to withdraw subjects. Patients can choose to withdraw from the study at any time. We will request that the patients notify the investigators if they wish to withdraw from the study. Subjects will stop the study if:

- 1) The subject voluntarily chooses to withdraw from the study.
- 2) The study investigator(s) may choose to discontinue patient from study if patient is experiencing adverse effects that cannot be managed by dose adjustments of the study agent.

16.2 Data collection and follow-up for withdrawn subjects. Patients will continue to receive full clinical services in our lysosomal disease treatment clinic.

16.3 Subject compensation. There will be no compensation to subjects for participation in this clinical trial.

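### No vital-status follow-up after removal from the study and no survival censoring rule, although the ITT endpoint is age at death or study conclusion

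*Combined protocol and SAP*

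**What the plan says.** Sections 12.1, 13.1 and 18.3 make overall survival in the ITT population the primary analysis, "evaluated based on chronological age at time of death or conclusion of study (whichever occurs first"). Section 18.1 puts every child who starts any part of the regimen under the study into that population. Withdrawal is not named as an end of observation.

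Section 21.2 lists reasons for participant discontinuation. Several of them end study participation itself:
- kidney problems: "Participants who develop kidney function problems while in this study will be withdrawn from this study";
- severe diarrhoea or weight loss that diet or dose changes cannot manage: "the patient will be removed from the study";
- pregnancy: "If a participant becomes pregnant while in this study, they will be withdrawn from this study";
- withdrawal by the investigator.

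Bleeding from low platelets, in the same list, stops miglustat only, so the section uses both concepts.

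On data from these children, 21.2 says: "All data acquired prior to termination for the reasons outlined below will be included in the primary analysis unless patient withdraws consent". It adds that a final visit will be attempted and that "participants will be followed clinically until, if applicable, all adverse events resolve". Section 16.2, whose title covers data collection and follow-up for withdrawn subjects, says only: "Patients will continue to receive full clinical services in our lysosomal disease treatment clinic".

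For a child too ill or weak to attend an annual visit, 13.1 says that this does not lead to withdrawal and that "the investigators will continue to follow them through telephone contacts with family members and health care providers". Section 17 also schedules calls for enrolled children generally, including every 3 months throughout. Neither section mentions children who have been removed.

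Sections 18.4 and 22.1 apply last observation carried forward (LOCF) to loss to follow-up, with sensitivity analyses. No section names a survival estimator or a censoring rule.

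**The concern.** An ITT survival endpoint that runs to death or study conclusion needs each child's vital status at study conclusion, whether or not the child is still treated. The plan makes no commitment to collect it once a child is removed. Two analysts could then derive different survival times for the same child: one stops the clock at removal, one carries the child forward as alive, and one looks for a later death in clinic records.

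This matters more here than in a randomised trial. The comparison is with fixed published medians, so no control arm shares the bias. There are 3 × 5 = 15 children in each sub-type, so three removals are 3/15 = 20% of a group. Uncontrollable weight loss or renal problems could plausibly mark a child at higher risk of death. If so, losing those children from follow-up would make survival look better than it was. Vital status that the protocol and consent form do not cover may also be hard to recover later.

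**Working it through.** **What the plan's own figures allow.** The sample size of 30 is 6 strata × 5 and was set by feasibility. The documents give no event count, power, withdrawal rate or hazard after withdrawal. No survival calculation in the plan can be reproduced, and the size of any bias has to be explored over assumed values.

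**Inputs from the documents.** Reference medians: 47 months (infantile) and 14.5 years = 174 months (juvenile), sections 12.1 and 18.3.

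**Assumptions.**
- Weibull age at death with shape k = 2.5.
- 10, 20 or 30% of children assigned to withdraw, at an age uniform over 12–36 months (infantile) or 72–144 months (juvenile). Some die first, so about 9, 17 and 26% (infantile) and 8, 16 and 24% (juvenile) actually withdraw.
- Hazard after withdrawal multiplied by HR = 0.5, 1, 1.5, 2 or 3.
- Delayed entry at enrolment not modelled.

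**Formulas.** Cumulative hazard H(t) = (t/λ)^k, with λ = median/(ln 2)^(1/k). For the infantile group λ = 47/0.8636 = 54.4 months. A child assigned to withdraw at age W has S(t) = exp{−H(W) − HR·[H(t) − H(W)]} for t > W. The group's true survival is (1 − w)·exp{−H(t)} plus w times that expression averaged over W. Kaplan–Meier with censoring at W estimates exp{−H(t)}, whose median stays at the reference value whatever the HR.

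**Check by hand (infantile, w = 0.2, HR = 2, W at the midpoint of 24 months).**
- H(24) = (24/54.4)^2.5 = 0.129; H(47) = ln 2 = 0.693.
- Withdrawn children: S(47) = exp{−0.129 − 2 × (0.693 − 0.129)} = exp(−1.257) = 0.285.
- Group: 0.8 × 0.5 + 0.2 × 0.285 = 0.457.

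So 45.7% are alive at 47 months, while the censored analysis reports 50%.

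**Bias in the median: censored at withdrawal minus full follow-up, in months (simulation, 200,000 children per scenario).**

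| Sub-type | Assigned to withdraw | HR 0.5 | HR 1 | HR 1.5 | HR 2 | HR 3 |
|---|---|---|---|---|---|---|
| Infantile | 10% | −0.9 | 0 | +0.6 | +1.1 | +1.7 |
| Infantile | 20% | −1.8 | 0 | +1.2 | +2.1 | +3.4 |
| Infantile | 30% | −2.8 | 0 | +1.8 | +3.2 | +4.9 |
| Juvenile | 10% | −2.8 | 0 | +2.1 | +3.5 | +5.7 |
| Juvenile | 20% | −5.8 | 0 | +3.9 | +6.9 | +11.3 |
| Juvenile | 30% | −9.1 | 0.1 | +6.1 | +10.5 | +16.1 |

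Direct numerical evaluation of the formulas agrees to within 0.1 month (infantile) and 0.4 month (juvenile).

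**Against sampling error.** With 15 infantile children, 20% assigned to withdraw and HR 2, the simulated 95% range of the median under full follow-up is about 33 to 59 months. A bias of 2.1 months is small beside that, but more children would not remove it.

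**If LOCF were applied to survival.** Carrying withdrawn infantile children forward as alive gives medians of about 49, 52 and 56 months at 10, 20 and 30%. That overstates the median by about 2 to 9 months even at HR 1, where censoring at withdrawal is unbiased.

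**The case against.** A reader might infer that removed children are certain to be censored at removal, that deaths after treatment failure go uncounted, and that survival is therefore overstated. The documents do not support this stronger reading:

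- The sentence in 21.2 says which data are included; it does not exclude later deaths. The endpoint wording can be read as follow-up to study conclusion. Censoring at removal is an inference from that sentence and from silence elsewhere.
- Disease progression and lack of efficacy are not listed as removal reasons in 13.9, 16.1 or 21.2, although the investigator's judgement of well-being in 13.9 could reach them. Sections 13.1 and 17 keep a child who is too ill to attend in the study. The most prognostic route to dropout is thus largely closed.
- Nothing links pregnancy to worse survival. Diarrhoea and weight loss are described as miglustat effects, and in the two infantile patients described in section 7.0 they resolved after dose reduction. The direction of bias is not established.
- Withdrawn children are offered continued care in the investigators' own clinic, so many deaths would probably become known.

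Most of this stands, and it makes the bias conditional. It does not close the gap. Knowing of a death through clinical care is not a commitment to record it and count it. The scheduled calls are not extended to removed children. The missing-data sections offer only LOCF and unspecified sensitivity analyses, neither of which defines a survival time.

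**Conclusion.** The point holds as a gap in follow-up and in the analysis rule. The plan removes some ITT children from the study, commits their data to the primary analysis only up to termination, plans no vital-status follow-up to study conclusion, and does not say how their survival time ends. That conflicts with the endpoint as defined.

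Whether the result is biased depends on the hazard after removal, which the documents do not give. Upward bias is the more likely direction if children removed for weight loss, renal problems or investigator concern are sicker. It is not proven. Under the assumptions above, the plausible upward range is about +0.6 to +5 months (infantile) and +2 to +16 months (juvenile). The bias is zero if removal is unrelated to prognosis, and about −1 to −3 and −3 to −9 months if removed children do better (HR 0.5). These sizes rest on assumed withdrawal rates, an assumed Weibull shape and no delayed entry.

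This should be fixed as a cheap improvement. It does not invalidate the design.

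**What to change.** Leave the clinical withdrawal rules as they are. In 16.2 and 21.2, separate stopping treatment from ending survival follow-up. For every ITT child whose family has not withdrawn consent for contact, collect vital status and date of death, or date last known alive, to study conclusion by the telephone route already in 13.1, and include it in the primary analysis.

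In 18.3 and 18.4 (and the duplicate text in 22.1), state that survival is censored only at study conclusion, withdrawal of consent for contact, or true loss to follow-up; that LOCF does not apply to survival; and that the number censored for each reason will be reported by sub-type.

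The cost is protocol and consent wording and an occasional call to a few families, with no added visits or procedures.
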